## **Nurse Case Management Intervention Phase 2 – Treatment Initiation:**

Date: May 8, 2017

Principal Investigator: [name], MPH, NP

Application Number: IRB00081068

This phase of the intervention will decrease time to HCV treatment initiation by using a nurse case manager to coordinate communication about antiretroviral therapy (ART) modifications between the patient, HCV provider documentation, and HIV provider. Participants who are enrolled in another clinical trial will not be included in this phase. Participants in clinical trials that provide medication (such as the CHAMPS study or an investigational drug trial) will receive an intervention to initiate HCV treatment within that trial. These participants are expected to follow a different timeline than clinical patients and face different challenges. Therefore, this phase will include a subgroup of consented Care2Cure study participants who link to an appointment at the Bartlett Specialty Practice HCV provider.

After the participant attends the Viral Hepatitis appointment, the research nurse case manager will review the HCV provider's note in the electronic medical record to determine what decision was made about initiating HCV treatment (defer or start). This phase will be single-blinded; no direct communication will occur between the research team and the HCV provider to avoid influencing the HCV management of the patient. The intervention will support the HIV provider and patient without influencing the HCV provider's decisions. Using a Phase 2 Algorithm, the research nurse case manager will identify participants who have a decision to start treatment indicated in the HCV visit note. The anticipated HCV therapy regimen(s) in the clinic note will be assessed for potential drug-drug interactions with the participants' current ART regimen. If a modification in ART is indicated because a contraindicated drug-drug interaction exists, the research nurse case manager will contact the participant via his/her preferred contact method to schedule a follow-up NCM visit. At this visit, the participant will be given a modified one-page drug interaction sheet tailored to his/her ART regimen. The research nurse case manager will also send a secure email to the participant's HIV provider notifying him/her of the potential need for ART modification. This email will include the latest DHHS "Concomitant Use of Selected HIV Drugs and FDA-Approved HCV Drugs for Treatment of HCV in HIV-Infected Adults" table 12. The table will serve as a decision-making aid for the HIV provider to modify the ART regimen if needed. The research nurse case manager will coordinate an ART modification appointment with the participant's primary HIV provider as needed so the patient does not wait the usual 3 to 6 months until his or her next scheduled HIV primary care visit.

To measure the effectiveness of NCM Phase 2, the electronic medical record will be reviewed 6 months after the enrollment visit. The study team will record whether a change in ART was made during the study period (yes/no). We will also determine if a prescription for HCV therapy was written during the study period, and the time to initiation of that prescribed treatment. The 6-month period for final data collection should be adequate to account for the various steps in HCV treatment preparation among PLWH: 1) linkage to care; 2) ART modification as needed; 3) rechecking the HIV viral load 4 to 8 weeks after modification to ensure viral suppression on new regimen; 4) HCV-related blood tests and imaging, and 5) uncontrollable factors such as appointment cancellations, rescheduling, and reimbursement.

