### 2. Objectives

The specific aims of the proposed RCT are to:

1. Test whether a nurse case management intervention will **increase linkage** of persons with HIV/HCV co-infection to an HCV treatment pathway via the Viral Hepatitis Center compared to enhanced usual care  
*H0:* A higher proportion of those who are randomized to the intervention arm will attend the Viral Hepatitis Clinic or enroll in an HCV-treating clinical trial within 60 days of randomization compared to those who receive enhanced usual care.
2. Determine if a nurse case management intervention will **decrease time to HCV treatment initiation** among persons with HIV/HCV co-infection compared to enhanced usual care

Date: May 8, 2017

Principal Investigator: [name], MPH, NP

Application Number: IRB00081068

*H0:* Those who are randomized to the intervention arm will have a decreased time to HCV treatment initiation from the point of randomization compared to those who receive enhanced usual care.

3. Describe the characteristics associated with uptake of HCV care among PLWH, controlling for covariates.

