### **Nurse Case Management Intervention Phase 1 – Linking to Care:**

Following informed consent, randomization, and completion of the baseline questionnaire, participants allocated to the intervention group will receive the first phase of the nurse case management (NCM) intervention (Table 1). This phase of the intervention will increase linkage to HCV care through NCM consisting of nurse-initiated referral, strengths-based HCV education, patient navigation, and HCV appointment reminders. The research nurse case manager will initiate an HCV referral for participants randomized to the

Date: May 8, 2017

Principal Investigator: [name], MPH, NP

Application Number: IRB00081068

intervention group via the electronic health record. This will send a cue to the HIV provider to approve the referral and minimize the barrier of non-referral by the provider. Participants will then receive brief strengths-based HCV education. Strengths-based education can improve knowledge and motivation to achieve health-related goals in PLWH. The research nurse case manager will help participants identify their strengths within the context of engaging in HCV care, including social support and engagement in HIV primary care. HCV education will include transmission, symptoms, treatment, and risk reduction. Participants will also identify barriers to linkage to care and form a plan with the research nurse case manager to minimize these barriers; this may include referrals to benefits counseling, substance use, mental health services, and the Johns Hopkins “Cure Club” HCV support group.

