## 7. Study Statistics

### Analysis:

Data will be cleaned and efforts made to minimize the effects of missing data. All provider visits at Johns Hopkins are registered in the electronic medical record, so absence of a registered appointment during the study period will be considered non-attendance for the primary outcome variable. A computer-based data collection method will be used for data collection of independent variables in attempt to minimize missing data. Exploratory and descriptive analysis will be completed for all study variables. Variables will be tested for normality and examined with means and standard deviations or medians and interquartile ranges accordingly. Baseline characteristics comparing the two groups (usual care vs. intervention) will be assessed. Any differences between the groups will be adjusted for in further analysis. The significance level will be set at 0.05. All tests will be two-tailed and analyzed by intention-to-treat.

**Primary Outcome:** The primary outcome is linkage to care, measured by attendance at the Viral Hepatitis Center (either traditional care or an HCV-treating clinical trial) within 60 days of randomization (yes/no). This hypothesis will be tested using a two-sample z-test for the difference in independent proportions comparing the intervention to usual care groups.

**Secondary Outcome:** The secondary outcome is time to HCV treatment initiation, measured by the number of days from randomization to the date HCV treatment is initiated according to the medical record. Kaplan Meier estimates will be conducted to compare time to HCV treatment initiation between participants in the intervention group and the usual care group, and a log-rank test will be used to test the difference. Covariates (age, sex, race/ethnicity, HCV knowledge, substance use, fibrosis score, CD4+ T cell count, HIV viral load, care giving responsibilities, and participation in Cure Club) will be included in the Cox regression model. To account for a time to treatment initiation greater than the observed time period of 6 months, right censoring will be implemented for participants who have not initiated HCV treatment at the end of the 6-month period.

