### **Sample Size Justification:**

Currently, 40% of new Viral Hepatitis Clinic appointments are attended by patients. Based on prior studies testing the intervention components in similar populations, including persons living with HIV and/or substance use disorders, it is expected that the intervention will improve the primary outcome of linkage to care by 18-30%. Although the effect size is not known in the context of HCV, we estimate an improvement in linkage of 20% (i.e., 60% attendance [0.60] in the NCM group compared to 40% attendance [0.40] in the usual care group) based on these prior studies. Using these figures and a two-tailed test with an alpha of 0.05, a conservative estimate of the total sample size required to achieve 80% power is 97 per group, or a total of 194 participants (G\*Power 3.1.9.2). With a sample size of 100 participants in each group, there should be an adequate number of participants to detect a difference in proportion of linkage to care for the primary aim.

For Phase 2, participants with successful linkage to clinical care from Phase 1 (those who attend  $\geq 1$  appointment at the Viral Hepatitis Clinic within 60 days) will be included. Therefore, the eligible sample size will be less than 40-60% of the original sample size because a linkage to care proportion of 0.40-0.60 is expected, and some participants will link to a clinical trial and not be included in this outcome. This is a secondary outcome and estimated effect size is unknown. However, with 100 participants in this group (half of the total sample size), we will have 90% power to detect a hazard ratio of 2.

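### The 6-month review is said to measure Phase 2, but the randomised comparison estimates only the two-phase programme

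*Combined protocol and SAP*

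**What the plan says.** Section 4, under Phase 2 – Treatment Initiation, describes the component's purpose: "This phase of the intervention will decrease time to HCV treatment initiation by using a nurse case manager". It then gives the reason for the final record review: "To measure the effectiveness of NCM Phase 2, the electronic medical record will be reviewed 6 months after the enrollment visit". The same paragraph justifies the 6-month window by listing the "various steps in HCV treatment preparation among PLWH: 1) linkage to care; 2) ART modification as needed", followed by viral load rechecks, work-up and administrative delays.

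The outcome is defined elsewhere. Section 7 (Secondary Outcome) has it "measured by the number of days from randomization to the date HCV treatment is initiated according to the medical record", tested by log-rank with a Cox model for covariates, censored at 6 months and analysed by intention-to-treat. Section 2, Aim 2, states that the intervention arm "will have a decreased time to HCV treatment initiation from the point of randomization compared to those who receive enhanced usual care".

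On Phase 1, Section 4 says that "participants allocated to the intervention group will receive the first phase of the nurse case management (NCM) intervention" and "This phase of the intervention will increase linkage to HCV care through NCM consisting of nurse-initiated referral". Table 1 places these elements at or before the HCV appointment, in the intervention arm only.

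The Sample Size Justification plans "60% attendance [0.60] in the NCM group compared to 40% attendance [0.40] in the usual care group". For Phase 2 it includes only participants who link to clinical care within 60 days and leaves out those who link to a clinical trial. That is a different analysis set from the intention-to-treat set in the Analysis section.

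**The concern.** The outcome presented as the measure of Phase 2 contains the step that Phase 1 is designed to change. If Phase 1 raises or speeds linkage, more intervention participants reach a treatment decision, and reach it sooner, even if ART coordination adds nothing. No analysis in Section 7 starts the clock at the HCV visit or otherwise separates the phases.

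What is at stake is interpretation. The Abstract describes nurse-initiated referral together with drug-interaction coordination as novel and untested. Readers interested in the coordination component may take Aim 2 as its test, and the Phase 2 sentence invites them to. The two definitions of the analysis set make this worse, because they answer different questions and respond differently to a Phase 1 effect.

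**Working it through.** **Plan's own figures.** With 0.40 v 0.60, two-sided 0.05 and 80% power, n = [1.96·√(2·0.5·0.5) + 0.8416·√(0.24 + 0.24)]² / 0.20² = (1.3859 + 0.5831)² / 0.04 = 96.9, so 97 per group, as stated. For 90% power at a hazard ratio of 2, the Schoenfeld formula gives 4(1.96 + 1.2816)² / (ln 2)² = 87.5, so 88 events (Freedman: 95). The stated 90% with 100 linkers is therefore reproduced only if nearly all of them start treatment within the window.

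**What the randomised contrast contains.**
- Randomised factor: the whole intervention arm v enhanced usual care (Section 4, Allocation).
- Received by that arm: Phase 1 at baseline, then Phase 2 for those who link to clinical care.
- Clock: from randomisation (Aim 2; Secondary Outcome).
- First step on that clock: linkage (Section 4, Phase 2).

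The contrast is therefore the Phase 1 effect on linkage plus any Phase 2 effect after linkage.

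**Size with a zero Phase 2 effect.** Linkage of 60% v 40% is from the plan. The share *q* of linked participants who start treatment within about 6 months is not given. I assume a range: 28% (7% initiated in the Abstract ÷ 25% attended in the Background) to 50% (the Background says fewer than half). Both sources are ever-treated figures, not 6-month rates.

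If *q* is the same in both arms, the 6-month start proportions are 0.60*q* and 0.40*q*. The hazard ratio implied by those cumulative proportions is ln(1 − 0.60*q*) / ln(1 − 0.40*q*):
- *q* = 0.28: ln(0.832) / ln(0.888) = 1.55
- *q* = 0.50: ln(0.70) / ln(0.80) = 1.60

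Rejection rates come from simulation: 100 per arm, exponential time from linkage to treatment with the same hazard in both arms, censoring at day 182. Link days are uniform on 7–60 in both arms unless stated.

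| Set and clock | Linkage | Hazard ratio | Log-rank p < 0.05 |
|---|---|---|---|
| All randomised, from randomisation | 60% v 40%, same timing | 1.55 (*q* = 0.28); 1.61 (*q* = 0.50) | 20%; 38% |
| All randomised, from randomisation | 50% v 50%, same timing (calibration) | – | 4.8% |
| Linkers only, from randomisation | 60% v 40%, same timing | about 1.0 | about 5% |
| Linkers only, from randomisation | 60% v 40%, days 7–23 v 20–60 (assumed) | about 1.24 | 8% to 11% |

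**Sensitivity.** A separate set of runs assumed that 30% to 90% start within 120 days of the visit. All-randomised rejection was 27% to 75% with equal linkage timing. In linkers only, with linkage at mean day 15 v 40 (assumed), it was 7% to 54%. Restarting the clock at the first HCV visit among linkers returned hazard ratios of 0.98 to 1.01 and rejection of 4.5% to 6.0%. That holds only because the simulated linkers are comparable between arms, which randomisation does not guarantee.

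None of the runs treats participants who link to clinical trials separately, or allows treatment without linkage or linkage after day 60.

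**The case against.** The strongest reply is that the hypothesis under test is already the whole programme. Aim 2 compares arms from randomisation, the Abstract's hypothesis names all the components together, and the Analysis section is intention-to-treat. This stands. A reader might infer that the Aim 2 test is invalid or has an inflated type I error; the documents do not support that. In the simulated trials the programme does speed treatment, so those rejections are true positives for Aim 2.

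Second, the Sample Size Justification limits Phase 2 to linkers, and there a higher linkage proportion alone creates no spurious effect. This also stands, so the 20% to 38% belongs to the all-randomised set only. It does not rescue the Phase 2 sentence: earlier linkage still shortens time from randomisation, and same-visit scheduling and reminders could plausibly bring visits forward. Linkers are also a post-randomisation subset whose make-up Phase 1 may change.

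Third, the statement that Phase 2 will shorten time to treatment describes the component's purpose, and the same section acknowledges linkage as a step. The review also records ART change (yes/no), and monthly logs record intervention dose. So it would be too strong to say that the plan credits the outcome to Phase 2 alone. These are process measures, however, with no between-arm analysis planned in Section 7.

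Finally, a reader might infer that a positive Aim 2 would lead the trial to recommend ART coordination by itself. Nothing in the documents says so.

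**Conclusion.** The point holds as one of attribution. The 6-month comparison is a valid randomised estimate of the two-phase programme and cannot measure the effectiveness of Phase 2, as the Phase 2 text says it does. In the intention-to-treat set, planned linkage alone would give a hazard ratio of about 1.55 to 1.6 and a significant result in about 20% to 38% of trials. This rests on the assumed 28% to 50% start rates, equal post-linkage hazards and equal linkage timing. In the linkers-only set there is no inflation with equal timing. The 8% to 11% there depends on an assumed shift in linkage days, and selection of linkers is a further, unquantified problem. The design fixes the direction of the all-randomised effect; the assumptions fix its size. The conflict between the two analysis sets needs settling in any case, because it determines which of these results applies.

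**What to change.** 1. In the Phase 2 text of Section 4, replace the statement that the review measures Phase 2 effectiveness with one saying that the randomised comparison of time to treatment estimates the effect of the two-phase programme.
2. Reconcile the Analysis and Sample Size Justification sections by making all randomised participants, by intention-to-treat, the analysis set for that comparison. State how treatment started within a clinical trial is counted, since the Sample Size Justification currently leaves those participants out.
3. Add a supportive two-step display by arm: cumulative incidence of linkage from randomisation, then of treatment start from the first HCV visit among those linked to clinical care. Give the second step a hazard ratio with 95% CI, label it non-randomised, and make no efficacy claim for Phase 2 from it.

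The cost is wording plus one figure, from dates already in the record. The primary analysis, visits and sample size do not change. The sponsor gives up a separate efficacy claim for Phase 2, which this design cannot support.

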Because appointment scheduling is a known barrier to linkage to care, patient navigation will include either a) calling central scheduling during the visit so the research nurse case manager can navigate participants through the Viral Hepatitis Clinic scheduling process or b) calling a clinical trial recruitment number to link eligible participants with an HCV-treating clinical trial. Participants also will be encouraged to call the Care2Cure research nurse case manager for needs relating to linking to HCV care throughout the study period. All contacts and amount of time spent with the study participants will be recorded by the research nurse. Participants will receive a personalized HCV appointment reminder in addition to the automated phone reminder all patients receive through the Johns Hopkins Hospital usual care system. A plan for contacting participants for personalized appointment reminder will be made, including the best mode of contact (phone, text, or email) and time of day. Participants will be contacted 1 day before their scheduled Viral Hepatitis Center appointment (either at the Bartlett Specialty Practice or a clinical trial) for an appointment reminder in addition to the automated JHH reminder 2 days before the appointment. If the scheduled Viral Hepatitis Center appointment is greater or equal to 2 weeks (10 business days) from the date of the baseline visit, participants will also be contacted one week before the appointment for a reminder.

The medical record will be reviewed 60 days after the baseline visit to verify whether the participant was registered for one or more Viral Hepatitis Clinic appointment since randomization if referred to the Bartlett Specialty Practice HCV provider. If the participant was referred to a clinical trial, attendance at a study appointment will be confirmed with that study coordinator.

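### Time to HCV treatment initiation has no assured route for capturing treatment started inside a clinical trial or outside Johns Hopkins, and the plan conflicts on whether trial-linked participants are analysed

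*Combined protocol and SAP*

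**What the plan says.** Section 7 (Analysis, Secondary Outcome) defines how the outcome is obtained; it is "measured by the number of days from randomization to the date HCV treatment is initiated according to the medical record". It adds that "right censoring will be implemented for participants who have not initiated HCV treatment at the end of the 6-month period". The same section states: "All tests will be two-tailed and analyzed by intention-to-treat". The second aim in Section 2 compares participants as randomised, and Table 1 marks the 6-month abstraction of treatment initiation as applying to all participants.

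The collection step is under NCM Phase 2 in Section 4: "the electronic medical record will be reviewed 6 months after the enrollment visit". What is collected is narrower than the Section 7 definition: "We will also determine if a prescription for HCV therapy was written during the study period", together with when such prescribed treatment began.

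The Phase 2 text also says that participants in medication-providing trials "will receive an intervention to initiate HCV treatment within that trial", and it leaves them out of Phase 2. For linkage, the Phase 1 text has a separate check for those referred to a trial: "attendance at a study appointment will be confirmed with that study coordinator". No matching check is written for the treatment start date. The exit interview covers barriers and satisfaction and names no start date. Treatment by an outside provider is not mentioned for this outcome.

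The Sample Size Justification describes a different analysis set: those who attend the Viral Hepatitis Clinic within 60 days, with participants who link to a trial left out of this outcome.

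**The concern.** A start that leaves no clinic prescription can be missed. If every randomised participant is analysed, as Section 7 requires, a treated person whose start is missed is censored at 6 months with the untreated. If instead trial-linked participants are dropped, the comparison is restricted by something that happens after randomisation and that the intervention is designed to change. Both readings can be drawn from the current text, and neither gives a clean estimate of the effect on time to treatment.

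The loss could differ by arm. The Phase 1 navigation step includes telephoning a trial recruitment number for eligible intervention participants, whereas enhanced usual care supplies a research hotline number. If that leads to more trial treatment in the intervention arm, and those starts go unseen, events are removed mainly from that arm. The plan itself counts trial access as a strength because trials reach patients at F0 and F1 who do not meet the stated Maryland criterion. Treatment of those patients is what is most at risk of not being counted.

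**Working it through.** **The plan's own power figure.** The Sample Size Justification gives 90% power for a hazard ratio (HR) of 2 with 100 participants. With two-sided alpha 0.05, (1.960 + 1.282)² = 10.51.

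- Schoenfeld: events = 4 × 10.51 / (ln 2)² = 42.04 / 0.4805 = 87.5, so 88.
- Freedman: events = 10.51 × ((2 + 1)/(2 − 1))² = 94.6, so 95.
- If all 100 participants are events, Freedman power is Φ(√100/3 − 1.960) = Φ(1.373) = 91.5%. Schoenfeld gives 93.4%.

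The figure therefore needs about 88 to 95 observed starts among 100 participants, which leaves little room for missed ones.

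**Effect of missed trial starts if all randomised participants are analysed.** From the documents: 100 per arm, and linkage of 60% vs 40%. Assumed, because the documents give no figures: 60% of linked participants start treatment within 6 months whichever route they take, the numbers linking through trials are as in the table, and every trial start is missed. Under constant hazards with censoring at 6 months, HR ≈ ln(1 − p₁)/ln(1 − p₀), where p is the proportion counted as starting.

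| Linked through trials (intervention vs control) | Starts counted | HR |
|---|---|---|
| No starts missed | 60 × 0.6 = 36 vs 40 × 0.6 = 24 | ln 0.64 / ln 0.76 = 1.63 |
| 10 vs 2.5 | 36 − 6 = 30 vs 24 − 1.5 = 22.5 | ln 0.70 / ln 0.775 = 1.40 |
| 20 vs 5 | 36 − 12 = 24 vs 24 − 3 = 21 | ln 0.76 / ln 0.79 = 1.16 |
| 10% of linked in each arm | 32.4 vs 21.6 | ln 0.676 / ln 0.784 = 1.61 |

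**Second set of assumptions.** True HR 2, 100 per arm, 20% of usual care treated by 6 months, so 1 − 0.8² = 36% in the intervention arm. Power uses Schoenfeld's formula.

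| Share of starts unseen (intervention vs control) | HR | Power |
|---|---|---|
| 0% vs 0% | 2.00 | 0.74 |
| 10% vs 10% | 1.97 | 0.67 |
| 20% vs 10% | 1.71 | 0.45 |
| 30% vs 10% | ln(1 − 0.252)/ln(1 − 0.18) = 1.46 | 0.24 |

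With usual-care initiation between 10% and 30%, the 30% vs 10% row gives an HR of 1.51 to 1.40. In both sets, unequal loss moves the HR, while equal loss mainly costs events.

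**If trial-linked participants are excluded instead.** Take 100 linked participants split 60:40 and assume 10% to 30% of them link through a trial, equally in both arms. That leaves 90 to 70. Power for HR 2 is Φ(ln 2 × √(0.6 × 0.4 × d) − 1.960), with d the number of events: 0.90 to 0.81 if every remaining participant starts treatment, and 0.62 to 0.52 if half do. The selection problem comes on top of this and is not measured by these figures.

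**The case against.** The strongest objection is that the plan does address trial-linked participants. The Sample Size Justification leaves them out of this outcome, and the Phase 2 text gives a reason: they follow another timeline and face other obstacles. The prescription wording sits in a paragraph about measuring Phase 2, which is limited to clinic-linked participants. On that reading they are excluded, not censored as untreated. This stands as a limit on the point: a reader might infer that all trial-treated participants will be scored as untreated, and the documents do not settle that. It does not remove the problem. The exclusion contradicts Section 7, the second aim and Table 1. It also does not cover someone who attends the clinic within 60 days and enters a trial later, or anyone treated elsewhere.

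A reader might also infer that trial treatment is invisible to the study. That is too strong. Section 7 refers to the medical record without limiting it to clinic prescriptions, the trials are within the Viral Hepatitis Center, and monthly logs cover encounters in the Johns Hopkins system in both arms. Trial dosing may well be recorded. But none of these sources names a first-dose date, and for linkage the plan chose to ask the coordinator rather than rely on the record.

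Finally, a reader might conclude that the bias against the intervention is established. It is not. All participants, whatever their arm, are asked about referral to a trial, and the text can be read as having the study nurse refer both arms. The navigation call makes a difference plausible, but no trial shares are given. The HR of 1.16 needs a third of intervention linkers (20/60) but an eighth of control linkers (5/40) to go through trials, with every one of their starts missed.

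**Conclusion.** The point holds as a gap in ascertainment combined with a conflict over the analysis population. The plan does not ensure capture of treatment started in a trial or outside Johns Hopkins, and Section 7 and the Sample Size Justification disagree on whether trial-linked participants are in the analysis. Settling the population in favour of all randomised participants would not by itself repair the capture of start dates.

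The size is conditional. If trial starts are missed more often in the intervention arm, an HR of 1.63 falls to about 1.40 to 1.16; with equal trial shares it stays at 1.61. These values rest on assumed initiation rates, trial shares and complete loss of trial starts. For treatment outside Johns Hopkins neither frequency nor direction by arm can be derived. The outcome is secondary and the primary linkage outcome is unaffected, so this is a change that should be made because it is cheap, not a flaw that undermines the trial.

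**What to change.** 1. Reconcile Section 7 with the Sample Size Justification: state that the secondary analysis includes all randomised participants, with the clinic-linked subgroup as supportive only.
2. In Section 7 and in the Phase 2 outcome paragraph of Section 4, define the event as the first HCV treatment from any source: clinic prescription, trial-supplied drug or outside provider. Use that date in the Kaplan-Meier, log-rank and Cox analyses.
3. For any participant in a trial, in either arm, obtain the treatment start date from the trial coordinator at 6 months.
4. Add one question to the existing 6-month exit interview, worded and asked identically in both arms: whether HCV treatment was started anywhere, and on what date.

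The cost is one more item for the coordinator, one interview question and a protocol amendment. The amendment is more than wording, because it settles what the outcome estimates, and the power statement written for the clinic-linked set would need restating. The remaining weakness is that outside start dates are self-reported and will be missing for participants who are not reached.
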